6.1 Monitoring

One monitoring visit will be done by the Charité Coordinating Center for Clinical Studies, comprising the following tasks:

- Checking the existence of study participants
- Checking the existence of informed consents
- Checking the completeness of the source data for one study participant

6.2 Harms

Harms, like pain, persisting erythema lasting for more than 30 minutes or possible irritant reactions, which occur immediately or after loading, will be documented as an adverse event.

Within this trial the following definitions of adverse events will be used:

Device Deficiency (DD)

Inadequacy of a medical device with respect to its identity, quality, durability, reliability, safety or performance.

Note: Device Deficiencies include malfunctions, use errors, and inadequate labelling. All Device Deficiencies that could have led to a Serious Adverse Device Effect shall be reported in accordance with Serious Adverse Event reporting procedures.

Adverse Event (AE)

Any untoward medical occurrence, unintended disease or injury, or untoward clinical signs (including abnormal laboratory findings) in subjects, users or other persons, whether or not related to the investigational medical device.

Note: This definition includes events related to the investigational medical device or the comparator. This definition includes events related to the procedures involved. For users or other persons, this definition is restricted to events related to investigational medical devices.

Adverse Device Effect (ADE)

Adverse Event related to the use of an investigational medical device

Note: This definition includes adverse events resulting from insufficient or inadequate instructions for use, deployment, installation, implantation, or operation, or any malfunction of the investigational medical device. This definition includes any event resulting from use error or from intentional misuse of the investigational medical device.

Serious Adverse Event (SAE)

Adverse Event that:

- i. leads to death;
- ii. leads to a serious deterioration in the health of the subject, that either resulted in;
 - a. a life-threatening illness or injury, or
 - b. a permanent impairment of a body structure or a body function; or
 - c. prolonged hospitalization; or,
 - d. medical or surgical intervention to prevent life-threatening illness or injury or permanent impairment to a body structure or a body function; or

Serious Adverse Device Effect (SADE)

Adverse Device Effect that has resulted in any of the consequences characteristic of a Serious Adverse Event.

According to the Guidelines on Medical Devices (European Commission 2010) the above listed definitions only apply for non-CE marked devices and Conformité Européenne CE marketed devices outside the intended use. The silicone dressings used in this study are already CE marketed and are used within the intended use. Therefore formal reporting modalities do not apply. However, (1) SAEs and (2) DD that might have led to a SAE will be reported not later than 2 calendar days to the manufacturer using the reporting form in Appendix 1.

7. Ethics and dissemination

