3.3 Eligibility criteria

Inclusion criteria

- Healthy female volunteers
- 65 to 80 years
- Body Mass Index 18.5 to 29.9 kg/m²
- Non-smoker of at least one year (including electronic-cigarettes)
- Informed consent
- Being free of any clinical dermatosis in the investigational area
- Intact sacral skin without scars
- Skin phototype I, II, or III (according to Fitzpatrick)
- No regular use of leave-on products on the sacral skin
- Willing and able to fulfil the study requirements

Exclusion criteria

- Disability to maintain in supine or prone position
- Acute diseases
- Known hyper-sensibility or allergy to the study product or any of its ingredients
- Extensive UV exposure 4 weeks before study inclusion
- Use of topical treatment on the investigational areas or systemic treatment within the 4 past weeks (topical hyaluronan, anti-inflammatory drugs, corticoids, retinoids, NSIDS etc.) that would interfere with assessment and/or investigational treatments
- Medical history of skin cancer
- History of established Diabetes mellitus, cardiac or renal insufficiency, COPD

- Chronic inflammatory skin disorders such as atopic dermatitis, psoriasis, lichen planus
- Participation in another study 4 weeks prior to study start

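### As printed, the SAE definition's only hospital criterion is prolonged hospitalization, so a short first admission that meets no other criterion would not be classed as serious

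*Combined protocol and SAP*

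**What the plan says.** Section 6.2 (Harms) of the combined protocol and SAP adopts a set of adverse event definitions for use in this trial. An SAE is an adverse event that causes death, or one that "leads to a serious deterioration in the health of the subject, that either resulted in" at least one of four listed results:

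- a: an illness or injury that threatens life
- b: lasting impairment of the body's structure or function
- c: "prolonged hospitalization"
- d: treatment, whether medical or surgical, given to avert a or b; this item closes on the word 'or'

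Nothing follows the final conjunction in d; the next item is the definition of a serious adverse device effect (SADE), which takes its consequences from the SAE list.

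The end of section 6.2 states that the dressings are CE marked and used as intended, so formal reporting modalities do not apply. It then keeps one expedited route, to the manufacturer: "1) SAEs and (2) DD that might have led to a SAE will be reported not later than 2 calendar days".

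Section 3.3 describes the population as "Healthy female volunteers" aged 65 to 80. Section 3.4 has them attend four visits of about 5 hours each and leave the site once the measurements are done.

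**The concern.** A hospital criterion that speaks only of prolongation suits people who are already in-patients. These volunteers come from home and go back to it. For them the hospital event most likely to need classifying is a new admission, and the list as printed does not name one.

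The classification matters because the expedited report depends on the SAE concept, and no other expedited route is described. An admission that staff place outside the definition would be recorded but would not have to reach the manufacturer within 2 calendar days. A misclassification might also go unnoticed: section 6.1 plans one monitoring visit, which checks that participants and consents exist and that source data are complete for one participant.

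**Working it through.** No arithmetic decides this point, and the plan gives no figure to reproduce. The check sets the definition against the population and the reporting rule.

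**Step 1. Are the definitions in force?** Section 6.2 adopts them for the trial. It later says that, under the European guideline it cites, they apply only to devices without a CE mark or to use outside the intended purpose. It still uses the term SAE as a reporting trigger and gives it no other meaning. The list is therefore the only basis staff have for deciding what to report.

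**Step 2. Who is exposed?** Section 3.7 plans 12 women and section 3.4 plans four visits each, so 12 × 4 = 48 visits, all as an outpatient. With at least 3 weeks between visits, each woman is in the study for at least 3 × 3 = 9 weeks. The adverse event definition covers events whether or not they are related to the device, so an admission for any cause in that time would need a seriousness judgement.

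**Step 3. What can criterion c capture?** The phrase allows two readings.

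| Reading of criterion c | Long first admission | Short first admission |
|---|---|---|
| Extension of an existing stay | not captured | not captured |
| A lengthy stay | captured, but no length is given | not captured |

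On the first reading the criterion is almost empty here, because a subject would already have to be in hospital when the event occurred. On the second it is usable but has no threshold. A short first admission falls outside c either way.

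**Step 4. What do the other criteria capture?** An admission is still serious if the event is fatal or if, through a serious deterioration, it meets a, b or d. Criterion d matters here, since it brings in admissions for treatment that prevents a life-threatening event or permanent impairment. What remains is a short first admission that meets none of these.

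**Step 5. What happens to that remainder?** It is an adverse event under section 6.2 and is recorded as one. It is not an SAE or a SADE, and it does not by itself trigger the 2-day report.

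**Step 6. Is the list complete?** Criterion c is complete as printed. Criterion d ends on a conjunction with nothing after it. Either the plan left the list unfinished, or an item was lost when the text was read from the PDF. The available text cannot settle which, and nothing shows that a lost item concerned admission.

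**The case against.** **The tempting stronger reading.** A reader might infer that any first hospital admission escapes the SAE definition. The documents do not support that. Death and criteria a, b and d still apply to admissions, and if c means a lengthy stay then a long first admission counts too.

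**The 2-day report does not rest on observed SAEs alone.** This stands. Device deficiencies that might have led to an SAE are a second trigger, and the note under the device deficiency definition in section 6.2 covers deficiencies that could have led to a serious adverse device effect. These routes do not require that a serious event occurred. They still borrow the SAE concept, so the wording of the list affects them as well.

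**The list breaks off, so a claim about what it omits is weaker.** This is fair. The point is therefore limited to the list as printed, and the unfinished ending belongs in the correction.

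**The documents do not say that a short admission ought to be serious.** This also stands. The cited guideline is not available here, so whether the wording departs from its source cannot be checked. What can be shown is that the one hospital criterion fits the plan's own population poorly and is ambiguous.

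**The consequence is small.** Agreed. The event is still recorded, only a report to the manufacturer is at stake, and no stopping rule or analysis in the documents uses the SAE class.

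**Conclusion.** The point holds as a drafting gap of low severity. As printed, a short first admission that is not fatal or life-threatening, causes no permanent impairment and needs no intervention to prevent these would be recorded as an adverse event. It would not be classed as serious and would not trigger the 2-calendar-day report.

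The conclusion rests on three assumptions: staff apply the list as written; any item lost after d does not deal with admission; and subjects are not normally in hospital when an event begins. An unrelated stay between visits is possible, which is why criterion c is called almost empty and not empty.

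The documents give no admission rate, so the number of affected events cannot be estimated. With 12 healthy volunteers and CE-marked dressings it is probably very small. The effect is on safety classification and the speed of reporting. The dressing comparisons, which section 5.2 limits to description, are unaffected. A reader should not infer that admissions would go unrecorded.

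**What to change.** In section 6.2, reword criterion c so that it covers a new in-patient admission as well as prolongation of an existing stay. This also removes the need to decide what prolonged means.

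Check the list against the source document after criterion d. Restore the missing item if there is one; otherwise delete the trailing conjunction and close the list.

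The cost is a few words in one section, with the ethics committee informed of the change as section 7.2 provides. Design, visits, data collection and analysis stay as they are. The downside is an occasional extra expedited report to the manufacturer, in a number that the documents do not allow anyone to estimate.

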7.1 Research ethics approval

An approval to conduct this study will be obtained from the local ethics committee of the Charité-Universitätsmedizin Berlin.

7.2 Protocol amendments

The ethics committee will be informed about possible study amendments.

7.3 Consent

Subjects meeting all of the inclusion criteria and none of the exclusion criteria must provide written informed consent prior to participation. The informed consent form (ICF) will meet the requirements proposed by the ethics committee of the Charité. Any study participants can withdraw her consent at any time without giving reasons.

